Specific aim 1: We will enroll a convenient sample of 15 participants who will use VR during first trimester surgical termination under local anesthesia in our clinic. Anxiety scores will be recorded before and after the procedure using a visual-analog scale. After the conclusion of the procedure, we will conduct semi-structured interviews to understand their overall experience with the VR device and software. We will ask patients to describe their experience in their own words and without prompting. This will then be followed by scripted probes regarding specific experiences with the VR use during the procedure and its effect on anxiety and pain. The interviews will be audio-recorded for analysis. We believe that this sample size will allow us to obtain thematic saturation to analyze patients' experiences.

Specific aim 2: After enrollment of the experimental group, we will enroll 15 patients receiving standard care in our clinic to compare the anxiety scores before and after the procedure. The enrollment of thirty patients will serve as a convenient sample in order to obtain an effect size. This data will help power further studies to determine the significance of VR on anxiety management.

ii) Participants:

We will screen patients over 18 years of age presenting to our obstetrics and gynecology clinic for first-trimester surgical abortion. Eligible patients must be English-speaking women seeking elective first trimester surgical abortion under local anesthesia. Patients will be excluded from the study arm if they have a history of motion sickness or vertigo, seizures or epilepsy, recent eye surgery, visual impairment, or claustrophobia. We will also exclude patients diagnosed or treated for anxiety in the past.

iii) Study setting:

The study will take place at the UCLA West-Medical Obstetrics and Gynecology clinic, which in the past year (from 1/1/2016 to 12/31/2016), has helped women receive a total of 160 first-trimester surgical abortions under local anesthesia. Due to the high volume of potential patients, we expect ease of enrollment.

iv) Virtual Reality:

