We will use a commercially available VR device, comprised of a phone, headset and headphones. The phone is inserted into the headset to act as the visual display that can create different three dimensional environments. The device will require a wireless internet connection to work effectively. The patient will choose the virtual reality experience she prefers. More information about VR can be found at: appliedvr.zendesk.com

v) Outcome measurements:

We will collect standard demographic information (age, pregnancy history, ethnicity, race, educational and income level) from all participants using standard cross sectional survey. For each patient who has used the VR experience during the procedure, a pilot period measurement tool (Appendix A) will be administered after the recovery period. We will conduct a qualitative semi-structured interview in a private room (Appendix B). Audio-recordings of the patient's experience will be collected.

Anxiety scores: To assess the effect of VR on managing anxiety, we will measure the patient's perceived anxiety through survey scoring. Preoperatively, two surveys will be administered—a modified Amsterdam Preoperative Anxiety and Information Scale (modified APAIS) (Appendix C) and a visual analog scale for anxiety (numerical score with 0=minimum score 10 =maximum score) (Appendix D). The visual analog scale will again be used after the procedure.

vi) Statistical analysis:

In our qualitative analysis, interviews will be recorded and transcribed verbatim, and analyzed for thematic content using the Dedoose online software platform. Two members of the research team will code each transcript independently, with discrepancies resolved by consensus. For the quantitative component, the VAS scores, descriptive analysis using means and proportions for each variable of interest will be performed. Patterns of missing data will be assessed and imputation methods will be considered if appropriate. We will use mean and standard deviations for each group to detect the effect size for future studies.

IMPACT STATEMENT

Despite various analgesic techniques, first trimester surgical abortion is associated with significant pain, and the perception of pain, especially during abortion, is nuanced and affected not only

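### Aim 1 is feasibility, but the plan counts no women approached, declining, not starting or completing VR, so the result is conditional on use

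*Combined protocol and SAP*

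**What the plan says.** Feasibility appears in the title and as the first specific aim in section b) Objectives and Specific Aims. The Impact Statement makes later, adequately powered studies depend on its being shown. Section b) explains Aim 1 as practicality together with the qualitative experience of users, explored by semi-structured interview.

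The passages that bear on who is counted are these:

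- Section i) Trial Design/Sample Size, Specific aim 1: "We will enroll a convenient sample of 15 participants who will use VR during first trimester surgical termination under local anesthesia". The number is justified by thematic saturation. On interviews: "After the conclusion of the procedure, we will conduct semi-structured interviews to understand their overall experience with the VR device and software".
- Section ii) Participants: "We will screen patients over 18 years of age presenting to our obstetrics and gynecology clinic for first-trimester surgical abortion". Exclusions specific to VR follow. No count of women screened, excluded or declining is planned.
- Section iii) Study setting: in 2016 the clinic "has helped women receive a total of 160 first-trimester surgical abortions under local anesthesia", and "Due to the high volume of potential patients, we expect ease of enrollment".
- Section iv) Virtual Reality: "The device will require a wireless internet connection to work effectively".
- Section v) Outcome measurements: "For each patient who has used the VR experience during the procedure, a pilot period measurement tool (Appendix A) will be administered", after recovery. The sentence before it, on demographics, covers both groups.
- Section vi) Statistical analysis: thematic coding of interviews; "For the quantitative component, the VAS scores, descriptive analysis using means and proportions for each variable of interest will be performed"; a general sentence on missing data and possible imputation; and group means and standard deviations for a future effect size.

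No section names a proportion accepting, starting or completing VR, or says what happens if a woman enrols and never starts. Appendices A and B are not among the supplied text.

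**The concern.** A feasibility study should show how many women offered the device agree to it, start it and finish with it. Here the sample is described by use, and the one structured tool is tied to use. Women who decline leave no trace in any planned output, and those who enrol and never start have no stated place.

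The Impact Statement says that, to the authors' knowledge, VR has never been offered to this population, so uptake is unknown. Section iv) names a technical dependency that could prevent a start. A report built as planned could describe good experiences among 15 users while leaving readers unable to tell whether most eligible women accepted VR or most refused it. That matters for planning a later study, and refusals that are not logged at the time are hard to recover.

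**Working it through.** **The plan's own figures.** 15 VR users + 15 controls = 30, which agrees with the stated total. The 15 is a convenience sample, so there is no power calculation to reproduce. The plan states no feasibility proportion either.

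**Inputs.** From the documents: 15 in the VR group and 160 procedures a year. All acceptance, eligibility and non-start figures below are assumptions.

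**Intervals.** For x out of n, the exact (Clopper-Pearson) 95% limits are the 0.025 quantile of Beta(x, n−x+1) and the 0.975 quantile of Beta(x+1, n−x). For x = n the upper limit is 100%.

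**Step 1: refusal.** Each row ends with the same 15 participants.

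| Accepted/approached | Proportion | Exact 95% CI |
|---|---|---|
| 15/17 | 88.2% | 63.6-98.5% |
| 15/30 | 50.0% | 31.3-68.7% |
| 15/75 | 20.0% | 11.6-30.8% |

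The last interval overlaps neither of the others, so a log would separate low uptake from moderate or high uptake. The first two overlap, so it would not reliably separate 88% from 50%. If recruitment stops at the 15th acceptor, exact negative-binomial limits are almost the same: 63.6-98.4%, 31.3-67.5% and 11.6-29.7%.

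**Step 2: can recruitment time replace a log?** If every eligible woman is approached, months to 15 acceptors = (15/p)/N × 12, with p the acceptance proportion and N the eligible women per year.

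- p = 0.5, N = 160: 30/160 × 12 = 2.25 months.
- p = 0.9, N = 80: 16.67/80 × 12 = 2.50 months.
- p = 0.2, N = 160: 75/160 × 12 = 5.6 months.

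Very low acceptance would slow recruitment. But 50% and 90% acceptance can give almost the same time when the eligible number is unknown, so time alone does not identify uptake.

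**Step 3: non-start.** With an assumed non-start rate r, the chance of at least one non-starter among 15 is 1 − (1−r)^15. This is 53.7% at r = 5%, 79.4% at 10% and 96.5% at 20%, so the case should be provided for.

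Suppose three women enrol and never start:

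- Kept among the 15: 12/15 = 80.0% (51.9-95.7%).
- Replaced, with all enrolled women counted: 15/18 = 83.3% (58.6-96.4%).
- Replaced, with the three left out: 15/15 = 100% (78.2-100%).

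The first two are practically equal. What matters is whether every enrolled woman is counted; keeping or replacing non-starters makes little difference.

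**The case against.** The strongest reply is that Aim 1 is defined in section b) as practicality and the experience of users, and that 15 was chosen for thematic saturation. On that definition, studying users is coherent. This stands for the experience part. It does not dispose of the rest: practicality is named too, and the Impact Statement treats feasibility as something to be established before further studies.

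A reader might infer that section v) deliberately denies the tool to non-starters. The text does not establish that. The word *only* is absent, the preceding sentence covers both groups, and the phrase may simply distinguish VR patients from controls. The interview sentence has no limit to users, so a non-starter who remains in the study could report the failure there.

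A reader might also infer that the plan would turn 80% into 100%. That needs enrolled women to go unreported, and nothing in the documents plans this.

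The missing-data sentence and the descriptive proportions could cover non-start, but they do not say so. They cannot reach a woman who declined before enrolment, because she is not in the data set. Appendix A is unseen and may contain items on device failure; that would not supply a count of women who refused. The expected ease of enrolment rests on clinic volume, which is not a measure of acceptance.

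**Conclusion.** The point holds as a gap in definition and reporting: feasibility is assessed conditionally on use, and no supplied section yields a denominator for refusal or a count of non-starters or completers. The numerical stake is the difference between uptakes such as 88% and 20%, which the planned outputs could not tell apart. These figures are illustrations resting on assumed counts, and they do not predict uptake in this clinic.

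The non-start part is weaker. It depends on a literal reading of section v), and once all enrolled women are counted the keep-or-replace choice moves the figure by only about three percentage points (80% to 83%) in the example. The documents do not support saying that device failures would be lost or that the plan is built to hide non-use. This is a worthwhile, inexpensive improvement, best made before enrolment.

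**What to change.** Add to sections ii) and v) a log of women screened, ineligible for VR, approached, accepting, declining (with reason, separating refusal of VR from refusal of research where possible), starting and completing. Define starting and completing in one line each. Record the reason for non-use for each enrolled woman who does not start.

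In section vi), report accepted/approached, started/enrolled and completed/enrolled, each with an exact 95% CI and described as imprecise at this sample size. State that every woman enrolled to VR is in the denominator, and say whether non-starters are replaced. Either choice is acceptable: replacement preserves 15 user accounts for the thematic analysis, while keeping non-starters leaves slightly fewer.

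The cost is a one-page log and a few sentences. If non-starters are replaced, a few extra women may need to be enrolled to reach 15 users. The resulting feasibility figure may look less favourable, and the intervals will stay wide.

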Studies have shown that VR is effective in reducing anxiety among a range of patients in differing circumstances, from patients undergoing dental procedures to patients undergoing chemotherapy.^{8,9} A recent randomized controlled trial has found that pre-operative VR can significantly reduce anxiety and increase patient satisfaction among patients undergoing craniotomy and spinal surgery.¹⁰ A study evaluating the feasibility of using VR among hospitalized patients revealed that most patients had positive experiences with VR and felt that it was not only capable of reducing anxiety but also pain.¹¹ Specifically, in the field of obstetrics and gynecology, a study showed that women undergoing episiotomy repair report markedly lower levels of anxiety after using VR as a form of adjunct pain therapy when compared to those who have not.¹² To our knowledge, the application of VR to first-trimester abortion has not been studied, and it is worthy of further research.

b) Objectives and Specific Aims:

1. *Assess the feasibility of using VR during first trimester surgical abortion under local anesthesia:*

Our work will assess the practicality and qualitative experience of women using VR during first trimester surgical abortion under local anesthesia. Semi-structured interviews will be conducted to understand the patient's experience of using VR.

2. Understand the effect of VR on procedure-related anxiety during first trimester surgical abortion:

We will analyze the anxiety scores of women before and after surgical abortion with the use of VR. In order to obtain an effect size for future studies, we will enroll a control group of patients receiving standard care and compare the anxiety scores between the two groups. The mean and standard deviation of anxiety scores for each group will be used to calculate power for future studies.

RESEARCH METHODS AND DESIGN

i) Trial Design/Sample Size:

We will conduct a mixed method pilot study to assess the feasibility of VR and understand its potential to decrease anxiety in the setting of first-trimester surgical abortion.

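### The Aim 2 effect size has no defined between-group contrast or baseline adjustment, and the planned summaries omit quantities that a change-based or baseline-adjusted future trial would need

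*Combined protocol and SAP*

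**What the plan says.** All references are to the combined protocol and SAP.

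- **Objectives and Specific Aims, aim 2.** Controls are enrolled to "compare the anxiety scores between the two groups", with no time point given. "The mean and standard deviation of anxiety scores for each group will be used to calculate power for future studies".
- **Trial Design/Sample Size, Specific aim 2.** Once the VR group is complete, "we will enroll 15 patients receiving standard care in our clinic to compare the anxiety scores before and after the procedure". The total of thirty is described as a convenience sample for obtaining an effect size.
- **Participants.** "Patients will be excluded from the study arm if they have a history of motion sickness or vertigo, seizures or epilepsy", and for certain other conditions. A further exclusion is not tied to one arm: "We will also exclude patients diagnosed or treated for anxiety in the past".
- **Outcome measurements.** Before the procedure patients complete a "visual analog scale for anxiety (numerical score with 0=minimum score 10 =maximum score"). Then: "The visual analog scale will again be used after the procedure".
- **Statistical analysis.** VAS scores are summarised descriptively, and "We will use mean and standard deviations for each group to detect the effect size for future studies".

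No randomisation is described, and enrolling all VR patients before any control rules it out.

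**The concern.** The one quantitative product of Aim 2 is a number to be carried into a later power calculation. With the VAS taken twice, per-group means and SDs could be those of the post-procedure score or of the change. These are different estimates with different SDs, and the plan does not choose between them or name a third, baseline-adjusted option.

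The groups may differ in anxiety at the start. They are recruited in different periods, and the VR-related exclusions are worded for the study arm only. The exclusion for past anxiety, which is not limited to that arm, narrows the scope for such a difference but does not remove it.

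Two things follow. A baseline difference can enter the planning estimate. And the listed summaries, followed literally, do not supply what is needed to size a trial analysed on change or with baseline adjustment.

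**Working it through.** **Inputs from the documents.** 15 per group (15 + 15 = 30, as stated), VAS before and after, VR group enrolled first. The documents give no alpha, power, SD, effect or correlation, so there is no sample-size figure to reproduce.

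**Assumptions, for illustration.** SD 1 at both times, within-group pre-post correlation r = 0.3 / 0.5 / 0.7, a 0.5 SD baseline gap, a 0.5 SD effect, two-sided 5%, 80% power.

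**1. How far the two readings can differ.** The post-score difference minus the difference in mean change equals the observed baseline difference exactly. With 15 per group its standard error is sqrt(2/15) = 0.365 SD. Chance alone therefore allows about ±1.96 × 0.365 = ±0.72 SD, before any selection or calendar effect.

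**2. Bias from a 0.5 SD baseline gap when VR has no effect.** In (a) the gap acts on the post score only through baseline. In (b) the gap is stable and present in full at both times.

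| Estimate | (a) formula | (a) r = 0.3 / 0.5 / 0.7 | (b) formula | (b) r = 0.3 / 0.5 / 0.7 |
|---|---|---|---|---|
| Post score | 0.5r | 0.15 / 0.25 / 0.35 | 0.5 | 0.50 / 0.50 / 0.50 |
| Change | -0.5(1 - r) | -0.35 / -0.25 / -0.15 | 0 | 0 / 0 / 0 |
| Baseline-adjusted | 0 | 0 / 0 / 0 | 0.5(1 - r) | 0.35 / 0.25 / 0.15 |

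A simulation with 15 per group (40,000 trials per cell) agreed with every entry to within 0.003 SD. Adjustment is less biased than the post score in both cases. Neither adjustment nor change is unbiased in both.

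**3. Future n per arm for the same raw 0.5 SD difference** (t-based, rounded up).

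| Basis | SD | r = 0.3 | r = 0.5 | r = 0.7 |
|---|---|---|---|---|
| Post score | 1 | 64 | 64 | 64 |
| Change | sqrt(2(1 - r)) = 1.183 / 1.000 / 0.775 | 89 | 64 | 39 |
| Baseline-adjusted | sqrt(1 - r²) = 0.954 / 0.866 / 0.714 | 59 | 49 | 34 |

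The pre and post means do give the mean change. The pre and post SDs alone do not give r, so they give neither the SD of change nor the residual SD.

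**4. Precision of the effect itself.** Suppose a 0.5 SD difference is observed.

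- Post score: 0.5 ± 2.048 × sqrt(2/15) = -0.25 to 1.25 SD.
- Adjusted, r = 0.5: 0.5 ± 2.052 × sqrt(2/15) × sqrt(0.75 × 27/26) = -0.16 to 1.16 SD.
- At the upper limits the implied n per arm is 12 (11.1 rounded up) and 10 (9.8 rounded up). At or below zero no n exists.
- By comparison, the Fisher z interval for r = 0.5 with standard error 1/sqrt(26) is 0.16 to 0.73. It moves the adjusted n only from 63 to 31 (62.1 and 30.1 rounded up).

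**5. Price of adjusting.** Mean width of the adjusted CI divided by that of the unadjusted post-score CI, by simulation:

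| r | 0 | 0.2 | 0.3 | 0.5 | 0.7 |
|---|---|---|---|---|---|
| Balanced baselines | 1.020 | 0.999 | 0.973 | 0.883 | 0.729 |
| True 0.5 SD gap | 1.054 | 1.032 | 1.005 | 0.913 | 0.753 |

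**The case against.** Four points deserve weight.

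- **The text leans towards pre-post.** The objectives and the design section both speak of scores before and after the procedure, and the same scale is repeated. A reader might infer that the plan commits to a post-only comparison. It does not: no sentence proposes one. This stands, and it lowers the chance of the worst reading. It does not close the gap, because the between-group sentence in the objectives names no time point and no change score is defined anywhere.
- **Regression is not shown to beat change.** A reader might infer that baseline-adjusted regression is the correct estimator here. The documents do not support that. Under a stable gap, change is unbiased and regression is off by 0.35 / 0.25 / 0.15 SD; in the other case the order reverses. Nothing in the plan says which case applies. This stands in full, so the two are treated as co-equal below.
- **The consequence is limited.** This is a descriptive feasibility pilot in a convenience sample, and the paired data would allow these quantities to be computed later. Both illustrative CIs in step 4 include zero, so no choice of contrast makes the effect precise. This stands and limits the severity. It does not excuse leaving the contrast open: choosing it after the data are seen can shift the estimate by the whole observed baseline difference.
- **Part of the remedy is nearly there.** Mean and SD at each time point is a natural reading of the descriptive plan. This is fair. What is new is the SD of change, residual SD, correlation and CIs.

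**Conclusion.** The point holds. Aim 2 is meant to deliver an effect size, but its between-group contrast is not defined and the pre-procedure VAS, though collected, is not used to adjust. The summaries named do not include the correlation, SD of change or residual SD needed to power a change-based or adjusted trial.

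In the illustration, the basis chosen moves future n per arm from 64 to anywhere between 34 and 89. A 0.5 SD baseline gap would put 0.15 to 0.50 SD of bias into an unadjusted post-score difference. These sizes rest wholly on the assumed r, gap, effect and equal SDs, since the documents give none of them.

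A reader might infer that the pilot risks a false-positive claim. It does not, because no test is planned. Nor does adjustment cure the design: confounding by enrolment period or arm-specific exclusions remains beyond what measured baseline anxiety captures. The amendment should be made, but the omission does not undermine the feasibility aim.

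**What to change.** In the Statistical analysis section, replace the effect-size sentence with text that does the following.

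1. Reports two co-equal estimates of the Aim 2 group difference, each with a 95% CI: the difference in post-procedure VAS adjusted for pre-procedure VAS by linear regression, and the between-group difference in mean change. Gives the reason: without randomisation neither is guaranteed unbiased.
2. Reports, by group, the mean and SD at each time point and the SD of change, together with the residual SD and the pooled within-group pre-post correlation with its 95% CI.
3. Bases any future sample size on the CI of the effect, not on the point estimate alone.
4. States that confounding beyond measured baseline anxiety remains.

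**Cost.** Analysis wording only, with no new data. The regression uses one degree of freedom. Its CI is about 2% (balanced baselines) to 5% (true 0.5 SD gap) wider than the unadjusted post-score CI if pre and post scores are uncorrelated. It breaks even at about r = 0.2 to 0.3 and is narrower above that.
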